1.2 Purpose

The purpose of the study is to investigate the potential optimization of the treatment with asciminib 80 mg total daily dose in adult patients with chronic myelogenous leukemia in chronic phase (CML-CP) previously treated with 2 or more TKIs.

Patient population:

Patients for this study will be identified based on warning criteria and resistance definition following ELN 2020 recommendations or intolerance on their 2nd TKI ([Hochhaus et al 2020a](#)). This is an expanded population compared to the original ASCSEMBL study as the inclusion criteria for the ASCSEMBL-protocol was based on the ELN treatment recommendations from 2013 ([Hochhaus et al 2020c](#)). Applying the newer ELN 2020 criteria will permit patients both with treatment failure as well as with warning signs to be included. This will allow for a population, with less advanced disease and lower risk of progression to enter the trial, which may benefit from a better and longer response to asciminib.

Patients treated with two or more TKI and intolerance to the last TKI treatment represent a clinical challenge as the number of treatment options available to them are limited. For the primary analysis, patients with intolerance will be eligible with BCR-ABL1 $\geq 0.1\%$ (i.e. not in MMR). Additionally, 30 patients who are intolerant to ongoing TKI treatment but in MMR will be allowed to enter the trial.

Simplified posology from b.i.d. to q.d. dosing:

The study will investigate the use of two different dose regimens: All patients will be randomized at baseline to receive 80 mg total daily dose of asciminib either as 40 mg b.i.d. in agreement with the dose investigated in ASCSEMBL or as 80 mg q.d. Though the trial will not be powered to compare both treatments, the descriptive data from both treatment groups is expected to provide additional insight into the optimal patient management.

Dose escalation:

Patients treated in later lines of CML often have few remaining therapeutic options. Asciminib has demonstrated activity and tolerability in dosages of up to 200 mg b.i.d. ([Hughes et al 2019](#)). With the limited treatment options available it is therefore of interest whether patients not in MMR at 48 weeks or thereafter could benefit from a potential dose escalation. Based on extensive PK modeling, a dose escalation from 40 mg b.i.d. / 80 mg q.d. asciminib to 200 mg q.d. asciminib was chosen for this approach.

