2.1 Data analysis general information

The planned analyses will be performed by Novartis. SAS version 9.4 or later will be used to perform all data analyses and to generate tables, figures and listings.

No formal interim analysis is planned for this trial. The following analyses are planned as detailed below.

- 48-week primary analysis: Formal testing of the primary endpoint will be performed. Analyses of other efficacy endpoints at and by week 48 and safety analyses will also be performed.
- 96-week analysis: Analyses of efficacy endpoints at and by week 96 and safety analyses will be performed.
- End of study treatment analysis is similar to the 96-week analysis without formal statistical testing. All efficacy and safety analyses will be included.

Except where categorically stated, all analyses, including the primary analysis will be conducted on **all** participant data (excluding the additional subjects who were intolerant to the last TKI and were in MMR at baseline). The purpose of having two randomized groups is not for comparison, but to provide data on different dosing regimens. Randomization is only used to have a balance in the allocation of treatment into either asciminib 40 mg b.i.d. or 80 mg q.d.

Data included in the analyses

The analysis data cut-off dates for the planned analyses are:

- 48-week Primary analysis: After all randomized subjects have been on study treatment for 48 weeks or discontinued earlier, i.e., LPFT + 48 weeks.

- 96-week analysis: After all randomized subjects have been on study treatment for 96 weeks or discontinued earlier, i.e., LPFT + 96 weeks.
- End of study treatment analysis: 30 days after the EOsT. (Note: After the study treatment period, every effort will be made to continue provision of the study treatment to subjects who in the opinion of the investigators are still deriving clinical benefit through alternative options if asciminib is not commercially available).

All statistical analyses will be performed using all data collected in the database up to the respective data cut-off date. All data with an assessment date or event start date (e.g. vital sign assessment date or start date of an adverse event) prior to or on the cut-off date will be included in the analysis. Any data collected beyond the cut-off date will not be included in the analysis and will not be used for any derivations.

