2.5.2 Statistical hypothesis, model, and method of analysis

The primary estimand will be analyzed based on the data from the FAS and according to the Intention-To-Treat (ITT) principle. Exact test for single proportion will be used at the one-sided 2.5% level of significance.

The null hypothesis is that the MMR rate at Week 48 is equal to 0.23. The alternative hypothesis is that the rate is greater than 0.23.

$H_0: \pi=0.23$ vs. $H_1: \pi >0.23$

where π is the major molecular response (BCR::ABL1 \leq 0.1% IS) rate at Week 48. MMR rate and its 95% confidence interval based on the Clopper-Pearson method will also be presented.

The null hypothesis will be rejected when the lower bound of the two-sided 95% CI is above 23%.

Summary statistics of MMR at week 48 will also be presented by randomized groups.

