2.7.1 Adverse events (AEs)

All the summary tables for adverse events (AEs) will be tabulated by randomized groups. AE summaries will include all AEs occurring during the on-treatment period. All AEs collected in the AE eCRF page will be listed along with the information collected on those AEs e.g. AE relationship to study drug, AE outcome, etc. AEs with start date outside of the on-treatment period will be flagged in the listings.

AEs will be summarized by number and percentage of subjects having at least one AE, having at least one AE in each primary system organ class (SOC) and for each preferred term (PT) using MedDRA coding. A subject with multiple occurrences of an AE will be counted only once in the respective AE category. A subject with multiple CTCAE grades or the same preferred term will be summarized under the maximum CTCAE grade recorded for the event. AE with missing CTCAE grade will be included in the 'All grades' column of the summary tables.

In AE summaries, the primary system organ class will be presented alphabetically and the preferred terms will be sorted within primary SOC in descending frequency. The sorting order for the preferred term will be based on their frequency in the asciminib 40 mg b.i.d. group.

The following adverse event summaries will be produced: overview of adverse events and deaths, AEs by SOC and PT, summarized by relationship, seriousness, leading to treatment discontinuation, leading to dose interruption/adjustment, requiring additional therapy, and leading to fatal outcome. The study treatment-related AEs/SAEs/AEs leading to treatment discontinuation as well as SAE with fatal outcome are summarized for the corresponding Safety set.

For posting to ClinTrial.gov and EudraCT, a summary table of on-treatment deaths and serious AEs and another summary table of non serious AEs, both including occurrences (an occurrence is defined as >1 day between start and prior end date of record of same preferred term) and sorted by SOC and PT, will be presented as well.

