2.7.2 Deaths

Separate summaries for on-treatment and all deaths (*including post-treatment deaths*) will be produced on the corresponding Safety set (SAF, SAF 2) by randomized groups, system organ class and preferred term.

All deaths will be listed, where deaths occurring during the post-treatment period will be flagged.

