2.7.4 Other safety data

2.7.4.1 ECG and cardiac imaging data

ECG

12-lead ECGs including PR, QRS, QT, QTcF, and RR intervals will be obtained locally for each subject during the study. ECG data will be read and interpreted locally.

The echocardiogram will be performed and evaluated locally to assess the left ventricular ejection fraction (LVEF).

Data handling

The average of the triplicate ECG parameters at each time point will be used in the analyses.

For unscheduled visits, ECGs that are reported on the same day and within 30 minutes apart from each other will be assumed to be sequential ECGs and thus will be used to compute the mean of the ECG parameters.

Unscheduled ECG measurements will not be used in computing the summary statistics for change from Baseline at each post-baseline time point. However, they will be used in the outlier analyses (e.g. QTc > 450 ms, > 480 ms, or > 500 ms at any time point, or an increase from Baseline in QTc > 30 ms or > 60 ms). End of treatment ECG measurements for discontinued subjects will be considered as an unscheduled measurement in case it occurs outside a scheduled visit.

Data analysis

The number and percentage of subjects with notable ECG values will be presented for the corresponding Safety set (SAF, SAF 2). Notable values are defined below:

- QT, QTcF
 - New value of > 450 and \leq 480 ms
 - New value of > 480 and \leq 500 ms
 - New value of > 500 ms
 - Increase from Baseline of > 30 ms to \leq 60ms
 - Increase from Baseline of > 60 ms
- HR
 - Increase from baseline >25% and to a value > 100 bpm
 - Decrease from baseline >25% and to a value < 50 bpm
- PR
 - Increase from baseline >25% and to a value > 200 ms
 - New value of > 200 ms
- QRS
 - Increase from baseline >25% and to a value > 120 ms
 - New values of QRS > 120 ms

A listing of all ECG assessments will be produced and notable values will be flagged. A separate listing of only the subjects with notable ECG values will also be produced. In each listing the assessments collected during the post-treatment period will be flagged.

Change from baseline ECG parameters by timepoint will also be summarized.

A listing of all LVEF assessments will be produced. In the listing, the assessments collected outside of on-treatment period will be flagged.

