2.10 Patient-reported outcomes

The patient reported outcomes (PRO) objectives are to compare the impact of treatment on PROs including CML-specific symptoms and health related patient quality of life from baseline through end of treatment in all subjects by using FAS except stated otherwise. The M.D. Anderson Symptom Inventory – Chronic Myeloid Leukemia (MDASI-CML) questionnaire is planned to be administered during screening, at weeks 4, 12, 24, 48, 72, 96, 120 and end of treatment.

The MDASI-CML is a 26 item self-administered questionnaire for adult CML patients. Twenty of the items measure the severity of disease-related symptoms and are scored from 0 (Not present) to 10 (As bad as you can imagine) and 6 items that measure symptom interference with daily life scored from 0 (Did not interfere) to 10 (Interfered completely).

The severity score will be calculated when a subject scores at least 11 items out of the 20 severity items using the formula: (sum of scores for the items answered) / (number of items answered). If a subject scores fewer than 11 items, the severity score will be missing.

The interference score will be calculated when a subject scores at least 4 items out of the 6 interference items using the formula: (sum of scores for the items answered) / (number of items answered). If a subject scores fewer than 4 items, the interference score will be missing.

For the severity score and interference score, descriptive statistics (n, mean, SD, median, 25th and 75th percentiles) will be provided for the actual scores and changes from baseline scores at each scheduled assessment time point.

Subjects with an evaluable baseline score and at least one evaluable post baseline score during the treatment period will be included in the change from baseline analyses. Missing data items in a scale will be handled according to the manual for each instrument. No imputation will be applied if the total or subscale scores are missing at a visit.

The additional subjects who were intolerant to the last TKI and were in MMR already at baseline will be assessed for the change in PRO from baseline by using FAS 2.

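### By-regimen summaries are specified for only some outputs, so the stated purpose of the two randomized groups is partly served: secondary molecular response, laboratory, ECG, vital-sign and MDASI-CML tables have none

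*SAP*

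**What the plan says.** SAP 2.1 gives the purpose of the randomization: "The purpose of having two randomized groups is not for comparison, but to provide data on different dosing regimens". Protocol 1.2 names the simpler once-daily posology as one of three topics of the study, alongside the patient population and dose escalation. It adds that "the descriptive data from both treatment groups is expected to provide additional insight into the optimal patient management". Both documents say that the trial is not powered to compare the regimens.

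The reporting default is also in SAP 2.1: "Except where categorically stated, all analyses, including the primary analysis will be conducted on" all participant data, leaving out the additional cohort already in MMR at baseline.

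By-regimen output is then stated in five places:

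- disposition and reasons for discontinuation (SAP 2.3.1)
- average daily dose, dose intensity and relative dose intensity (SAP 2.4.1)
- the primary endpoint (SAP 2.5.2): "Summary statistics of MMR at week 48 will also be presented by randomized groups"
- adverse events (SAP 2.7.1): "All the summary tables for adverse events (AEs) will be tabulated by randomized groups"
- deaths (SAP 2.7.2), where summaries "will be produced on the corresponding Safety set (SAF, SAF 2) by randomized groups, system organ class and preferred term"

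Elsewhere the text names an analysis set but no regimen split. For MDASI-CML, SAP 2.10 describes the analysis as running "from baseline through end of treatment in all subjects by using FAS except stated otherwise".

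**The concern.** If the randomized groups exist to supply data on each regimen, the reader expects the main descriptive tables to show each regimen. A programmer who follows the SAP as written would build one combined column for secondary molecular response, laboratory and liver tests, ECG/QTcF, vital signs and MDASI-CML.

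Some of these outputs are where two regimens with the same daily dose but different concentration profiles could separate. A higher peak bears on post-dose QTcF and laboratory values. A lower trough bears on early molecular response. Protocol 4.2 predicts from modelling that neither matters much. The randomized data could test that prediction descriptively, but a combined table cannot.

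The primary inference is not at stake. What is at stake is how much the trial reports about a topic it set out to describe.

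**Working it through.** **1. The plan's own figure.** The concern rests on no power figure, but the design was reproduced to confirm that the fix leaves it alone. For n = 156 and a null rate of 0.23 (SAP 3), the smallest r with P(X ≥ r) ≤ 0.025 is 47. The exact one-sided alpha is 0.0241, the power at 0.33 is 0.801, and the Clopper-Pearson lower bound for 47/156 is 23.05%. The stated 80% is confirmed.

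**2. Where regimen columns are specified.**

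| Output | SAP section | By regimen? |
|---|---|---|
| Disposition, discontinuation reasons | 2.3.1 | Yes |
| ADD, DI, RDI | 2.4.1 | Yes |
| Week 48 MMR | 2.5.2 | Yes |
| AE summary tables | 2.7.1 | Yes |
| Deaths | 2.7.2 | Yes |
| Secondary molecular response, time to and duration of MMR, CCyR, TTF/PFS/OS | 2.6.2 | Not stated |
| Laboratory and liver tests | 2.7.3 | Not stated |
| ECG/QTcF, LVEF | 2.7.4.1 | Not stated; ECG is split by escalation status only |
| Vital signs | 2.7.4.3 | Not stated |
| MDASI-CML | 2.10 | Not stated |

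**3. How the regimens differ.** Simulated means, q.d. against b.i.d. (Protocol Table 4-1):

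- AUC0-24hr: 12646 / 12638 = 1.001
- Cmax: 1463 / 908 = 1.61, about 61% higher
- Cmin: 215 / 302 = 0.71, about 29% lower

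Protocol Table 8-6 places triplicate ECGs 2 to 3 hours after dosing at Weeks 1 and 2, so the relevant data are already collected.

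**4. Dilution (hypothetical).** With 1:1 allocation, 156 / 2 = 78 per regimen. If events occur on one regimen only, the combined proportion is half the regimen's proportion. The documents give no event rates, so the counts below are assumed. Take, for example, a QTcF increase of more than 30 and up to 60 ms:

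| Events on one regimen, none on the other | That regimen (n = 78) | Combined (n = 156) |
|---|---|---|
| 4 | 5.1% | 2.6% |
| 6 | 7.7% | 3.8% |
| 8 | 10.3% | 5.1% |

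For a mean change with equal groups, the combined mean is the b.i.d. mean plus half the difference. A 10 ms difference thus shifts the combined mean by 5 ms above the b.i.d. mean, whatever that mean is.

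**5. Precision of a regimen column (Clopper-Pearson 95%).** 26/78 gives 23.1% to 44.9%, against 25.4% to 40.7% for 51/156. 8/78 gives 4.5% to 19.2%, and 4/78 gives 1.4% to 12.6%. At a rate near 33% that is about ±11 points per regimen against about ±8 combined, which is adequate for description.

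**6. What the AE tables catch.** Under Protocol 10.1.1, an abnormal laboratory or test result is an AE only if it causes symptoms or signs, is judged clinically significant, or needs treatment. The programmatic laboratory grades (SAP 2.7.3) and QTcF categories (SAP 2.7.4.1) have no such condition, so some will not reach an AE table.

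**The case against.** The case on the other side has several sound parts.

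- **The SAP never says that it pools the regimens for these outputs.** The sentence in SAP 2.1 defines which patients are analysed, not table columns. SAP 2.1.1 defines the treatment groups as the two regimens, and a time-to-MMR censoring rule in 2.6.2 refers to the treatment group. This stands: combined reporting follows from the default plus silence. But naming by-regimen output in five places suggests that other tables lack it, and one sentence would settle the matter.
- **The main results are already by regimen.** A reader might infer that the regimen question goes largely unanswered or that the randomization is wasted. The documents do not support that: the primary endpoint, all AE tables, deaths, discontinuation reasons and dose intensity are covered. The SAP also matches the protocol, which asks for by-group tables only for Week 48 MMR (12.4.2) and for AEs and deaths (12.5.2). No readable objective in Table 2-1 concerns regimen, although the exploratory ones are redacted.
- **Important signals have another route.** ECG findings judged clinically significant are recorded as AEs (Protocol 8.4.3). A confirmed QTcF above 500 ms, or more than 60 ms above baseline, requires interruption (6.6.3.1), and AEs leading to interruption are tabulated. This largely stands for severe events. It does not cover smaller shifts or laboratory grades that never become AEs.
- **The modelling predicts similarity.** Protocol 4.2 predicts similar efficacy and finds no apparent exposure-safety correlation between the regimens on any PK metric. This is a fair caution against expecting a difference. QTcF is not among the safety endpoints listed there, and a model prediction is a reason to show the randomized data.
- **MDASI-CML is not a convenience measure.** It scores symptom severity and interference. A reader might infer that a convenience benefit of q.d. is lost in the PRO tables; the instrument could not show one. The reason to split it is symptom burden by regimen.

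**Conclusion.** The point holds as a partial gap. By-regimen summaries are specified for disposition, dose intensity, Week 48 MMR, AEs and deaths. Under the all-participant default they are not specified for secondary molecular response, laboratory and liver tests, ECG/QTcF, vital signs or MDASI-CML, so the purpose given in SAP 2.1 is only partly served.

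The gap matters because simulated peak and trough differ by about +61% and −29% at equal AUC, and because laboratory and ECG changes that are not AEs would not be seen by regimen. The halving in a combined table assumes equal groups and events on one regimen only; it illustrates dilution and does not forecast a signal.

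The absence of a formal comparison is by design and is not an error. Alpha, power, the estimand and data collection are unaffected. The change is worth making before the first database lock, by which SAP 1 says all analysis decisions have been made, so that the choice of regimen tables does not follow the results.

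**What to change.** Add to SAP 2.1 that the following are shown by randomized regimen (40 mg b.i.d., 80 mg q.d.) and in total, descriptively and without testing:

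- efficacy summaries through Week 48
- MDASI-CML severity and interference scores
- laboratory and liver-test summaries
- ECG/QTcF summaries, including the Week 1 and Week 2 post-dose ECGs
- vital-sign summaries

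Through Week 48 these columns are free of escalation, because the earliest escalation is at Week 60 (Protocol Table 6-2, footnote). After Week 48, keep columns by randomized regimen for all patients and flag escalation status. Any summary limited to data before the first 200 mg dose should be labelled as selected: escalation follows failure to reach MMR or its loss, so what remains tilts towards responders.

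The cost is SAP wording and more table columns on data already collected, each labelled non-comparative.
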